The Legacy trial investigated the effects of diet intervention (20). The study followed 355 participants with Body Mass Index (BMI) 27 kg/m^2 or greater that participated in a weight loss program; 38% of the participants sustained a weight loss 10% of total body weight or greater. Greater than 10% weight loss resulted in a six-fold reduction in the recurrence of AF and improved cardiovascular risk factors compared to those who lost less weight and whose weight loss fluctuated (20).

Obstructive sleep apnea (OSA) is known to be highly prevalent in AF (27). A meta-analysis looking at both cohort and randomized trials of continuous positive air pressure (CPAP) for OSA in patients with AF resulted in a 42% low risk of AF recurrence (28). Thus, CPAP treatment for moderate or greater sleep apnea combined with exercise and diet may improve AF outcomes.

A major limitation of previous AF trials is lack of randomization and short duration of follow-up. In addition, no studies have investigated an intervention program that combines supervised exercise sessions, regular, structured diet and lifestyle education sessions, and risk factor management. There have been no meta-analyses on the effects of exercise and diet on AF symptoms given that there exist only a handful of studies to date. A Cochrane review (29) of randomized controlled exercise interventions in AF patients reported no differences in mortality and quality of life, and reported only small differences in exercise capacity, but the review did not evaluate symptom severity of AF nor did they measure reductions in risk factors commonly associated with AF. The review suggested a need for more randomized clinical trials (given that only six were included in this initial review) (29). Not only are there very few lifestyle intervention studies on AF, no studies have compared a structured in-hospital diet and exercise program *versus* a home-based exercise and diet program. We do not know whether positive effects are sustained once supervised interventions are terminated; nor do we know the necessary intensity to achieve and sustain target reduction in cardiovascular risk, left atrial remodeling, and AF burden.

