Richmond Hospital has successfully run a Cardiac Rehabilitation program for over 20 years. The 8-week program includes supervised exercise sessions (two per week), in conjunction with diet and stress management classes (one each per week). The program has reported low voluntary dropout rates (e.g., two dropouts of 100 patients in the last six months of the program). At present, cardiologists do not typically refer patients with AF to cardiac rehabilitation. For the current project, during the first six months (Phase 1) we plan to extend the duration of the existing Cardiac Rehabilitation exercise program to three months and we plan to use moderate to high intensity interval training combined with resistance exercises as per current literature in exercise and patients with AF. In addition, study participants will receive a heart rate and step tracker to guide intensity and duration for a home-based walking program and will maintain a minimum of 10 to 20 minutes of total body resistance training at home.

Richmond also has a successful bariatric surgery program where 200 patients per year are treated first with diet therapy, followed by mainly laparoscopic sleeve gastrectomy. Similar to the Legacy study described above, we will enroll participants with BMI greater than or equal to 27 kg/m^2 in a diet intervention run by dietitians from the Richmond Bariatric program. The goal of the nutrition component will be to reduce total body weight by at least 10%. The diet intervention will be an individualized, healthy diet program promoting reduced carbohydrate content, smaller portions, and mindful eating (30). During months six to twelve of the intervention (Phase 2), participants will continue with a home-based aerobic exercise program combined with resistance training that was learned in the hospital cardiac rehabilitation program. Participants will monitor their sessions using the heart rate and step tracker along with self-reported exercise logs. Motivated participants are free to join a community gym. The individual exit diet counseling will encourage participants to follow the final diet prescribed.

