- a. Left atrial remodeling will be measured by LA volume index, diastolic function grade, and estimate of LA pressure via echocardiography at baseline and one year follow-up.
- b. Cardiovascular risk factors will be compared at baseline, six months and one year. These include: Systolic Blood Pressure, Hemoglobin A1C (marker of average blood sugar over 3 months), body mass index, waist circumference, and low density lipoprotein (LDL cholesterol), apnea hypopnea index (AHI), and fitness classification (metabolic equivalents (METS) achieved on exercise stress test).
- c. Using pharmanet data, total cost of all medications and specific cost for antiarrhythmic agents, antihypertensive agents, diabetes and cholesterol lowering medications will be recorded and compared at baseline and one year. Hospital Emergency visits will also be compared.

5. Methodology

5.1 Proposed Study Design: This is a parallel-group randomized controlled trial. Consecutive patients meeting eligibility criteria that are seen for routine cardiology follow-up, or those referred by family physicians, will be invited to participate in this study. Patients who accept the possibility of a year-long diet counseling and exercise program will be randomized and stratified to ‘control arm’ *versus* ‘intervention arm.’ Forty patients will be randomized to control arm and 40 patients randomized to the intervention arm. Intervention will include Phase 1, a six month program including three months of diet counseling combined with home exercise, followed by three months (starting at week 13) of an in-hospital, Cardiac rehabilitation exercise program. Phase 1 also includes risk factor management by an internist who specializes in cardiovascular risk factors. Phase 2 of the intervention will include six months of home-based maintenance exercise and diet (starting at week 25). Assuming approximately 40% of eligible patients agree to participate (based on our experience that there is a high willingness to participate in both research studies and the cardiac rehabilitation program), and given that we were able to recruit 200 research participants in one year for a previous study (35), we estimate that it is feasible to recruit a total of 80 participants over a three to six month period.

5.2 Participants: Patients will provide written, informed consent. All study procedures will be reviewed and approved by the UBC Clinical Ethics board and the VCH operational approval process.

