Inclusion Criteria: Patients with paroxysmal, non-permanent, non-valvular AF who have a $BMI \geq 27 \text{ kg/m}^2$, or central obesity using abdominal circumference with ethnicity-specific values recommended by Canadian diabetes association (36); plus one of hypertension, diabetes, moderate or severe sleep apnea, or consumption equal to or greater than three glasses of alcohol per day. Participants must be over 18 years of age and under 75 years.

Exclusion Criteria: Patients with permanent AF, estimated survival less than 2 years, left ventricular ejection fraction $< 40\%$, and/or prior cardiac valve surgery. Other exclusions include: inability to walk on a treadmill, defibrillator, entry exercise test positive for ischemia (37), and/or absolute and relative contraindications to exercise testing (37).

5.3 Study Procedure: All participants will undergo baseline, maximal effort exercise testing described in data collection section 5.4. Peak heart rate (HR_{peak}), total METS, and Borg rating of perceived exertion scale will be recorded (37). Maximal exercise tests will be repeated at six months and one year in all participants. All participants in the intervention and control arms will be screened for obstructive sleep apnea with a home sleep apnea test (level three study). [name] (Respirologist at Richmond hospital) will assess any patients with at least moderate sleep apnea, an apnea hypopnea index over 20. [name] has expertise in sleep apnea and is a co-investigator of this study. CPAP will be recommended and for one year for patients with apnea hypopnea index of > 30 , or > 20 with excessive day time sleepiness. CPAP machines will be loaned by the sleep clinic to patients who do not have insurance coverage for one year. LA volume index, pressure and grade of diastolic dysfunction will be measured by echocardiography at baseline and one year. The same technician will perform all echocardiograms using the same echocardiogram machine, and one cardiologist blinded to participant’s study arm will review the results.

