5.4 Data Collection

All measurements (save demographics and medical history) will be collected at baseline, six months, and one year in both groups.

1. Patient demographics: age, sex, ethnicity, education, income, and living situation.
2. Medical history: medications and cost; hospital emergency visit and admission < 1yr, known coronary artery disease defined by prior myocardial infarction or presence of 50% stenosis on CT or invasive angiogram; admission for heart failure, prior stroke; average daily glasses of alcohol, smoking status (including frequency and amount); the Canadian Cardiovascular Society Severity in Atrial Fibrillation (CCS-SAF) Scale, (31) the Atrial Fibrillation Symptom Severity Scale (AFSS) (32), the 36-item Short Form Survey Instrument (33) and the EQ-5D-3L (34).
3. Anthropometrics: Body mass index (BMI), waist circumference, neck circumference, modified mallampati score (41) and blood pressure.
4. Blood work: Hemoglobin AIC, total cholesterol, creatinine, low-density lipoprotein, high-density lipoprotein, triglycerides, ALT, c-reactive protein, electrolytes, and brain natriuretic peptide.
5. Level 3 home sleep study: Apnea-hypopnea index, minimum saturation, and time spent with saturation < 90%, Epworth Sleepiness Scale (42).
6. Godin's leisure time physical activity measure will be used measure baseline physical activity levels (43).
7. Exercise Stress Test at maximal effort: Maximum METs achieved, peak heart rate, and rating of perceived exertion.
8. 48-hour Holter monitor: 48-hour heart rhythm monitor to determine frequency and duration of AF measured as the percent of time in AF.
9. Echocardiography at base line and one year: measurements: LA volume, LA pressure, diastolic function, grade, calculated biplane LVEF, and left ventricular hypertrophy.

All data sheets are attached in section 9 of the application. There is a data sheet for each: sleep study, echo, blood work, stress test, physical exam, and Holter monitor.

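### The denominator of LA volume index, the only atrial-size outcome, is not stated; if it is current body surface area, the targeted weight loss would bias it against the intervention

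*Combined protocol and SAP*

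**What the plan says.** Section 4 (Objectives, secondary outcomes, item a) lists three LA measures. It begins "Left atrial remodeling will be measured by LA volume index" and goes on to add the grade of diastolic function and an echocardiographic estimate of LA pressure, all at baseline and one year. Section 5.3 (Study Procedure) repeats the set: "LA volume index, pressure and grade of diastolic dysfunction will be measured by echocardiography at baseline and one year". Neither place gives a denominator, a formula, or the date of the body size to be used. Section 5.4 (Data Collection), item 9, lists volume itself: "Echocardiography at base line and one year: measurements: LA volume, LA pressure, diastolic function, grade". Unindexed volume is therefore collected but not named as an outcome.

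On weight, the section on the current state of knowledge says: "The goal of the nutrition component will be to reduce total body weight by at least 10" percent. That component belongs to the intervention arm. Section 5.3.1 gives controls usual care, a step tracker and a physical activity handout. Section 6 expects weight loss to be greater with the intervention than in controls.

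On analysis, the data analysis section compares arms by independent t-tests on differences from baseline. It states no adjustment for change in body size.

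**The concern.** An outcome that is a ratio can move because its denominator moves. Here the denominator, on its usual reading, depends on body weight, and the intervention is designed to lower body weight in one arm. The index would then carry two effects of opposite sign: any true shrinkage of the atrium, which lowers it, and the smaller body surface area, which raises it. The better the diet works, the larger the second effect.

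What is at stake is the between-arm contrast on the only named measure of atrial size. A modest true reduction in volume could be diluted or cancelled. Randomisation does not help, because the distortion arises after randomisation as a consequence of treatment. Blinded reading on a single machine protects the volume measurement but not the division that follows.

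**Working it through.** The plan gives no expected value, SD or power figure for LA volume index, so there is no stated figure to reproduce. Its sample-size figures concern fitness and time in AF and do not bear on this point.

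**Inputs from the documents**
- Weight-loss goal in the intervention arm: at least 10%.
- Evidence on how often such a goal is met, from the weight-loss cohort that the plan cites: "38% of the participants sustained a weight loss 10% of total body weight or greater".
- Echo at baseline and one year; between-arm t-test on change.

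**Assumptions, not in the documents**
- The index is LA volume divided by body surface area (BSA), recalculated at each echo.
- Height is constant. BSA is then proportional to weight^b, with b = 0.425 (Du Bois) or 0.5 (Mosteller).
- w is the between-arm difference in fractional weight loss. For simplicity, control weight is taken as unchanged.

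**Step 1. Change in the index with an unchanged atrium: (1 - w)^(-b) - 1**

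| w | BSA ratio, Du Bois | BSA ratio, Mosteller | Rise in index |
|---|---|---|---|
| 5% | 0.95^0.425 = 0.978 | 0.95^0.5 = 0.975 | +2.2% to +2.6% |
| 10% | 0.90^0.425 = 0.956 | 0.90^0.5 = 0.949 | +4.6% to +5.4% |

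The Haycock formula (b = 0.538) extends the upper end to +2.8% and +5.8%.

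**Step 2. What a true 10% fall in LA volume would look like: 0.90 / (1 - w)^b - 1**
- w = 5%: 0.90/0.978 gives -8.0%; 0.90/0.975 gives -7.7%. About 2.0 to 2.3 of the 10 percentage points are lost, or a fifth to a quarter.
- w = 10%: 0.90/0.956 gives -5.9%; 0.90/0.949 gives -5.1%. About 4.1 to 4.9 points are lost, or two-fifths to a half.

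**Step 3. True fall in volume that would show as no change: 1 - (1 - w)^b**
- w = 5%: 2.2 to 2.5%.
- w = 10%: 4.4 to 5.1%.

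**Step 4. Absolute scale, for an assumed baseline index of 30 to 45 mL/m2**
- w = 5%: +0.7 to +1.2 mL/m2.
- w = 10%: +1.4 to +2.4 mL/m2. With an assumed SD of change of 5 to 10 mL/m2, this is 1.4/10 = 0.14 to 2.4/5 = 0.48 SD against the intervention.

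**Step 5. Alternatives.** With unindexed volume, volume over height, or volume over baseline BSA, the denominator does not depend on follow-up weight. The artefact is then 0% at any w.

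**The case against.** Five points can fairly be made on the other side.

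- **The denominator is not in the text.** No passage mentions BSA, and the echo data sheet attached to the ethics application was not among the supplied documents. A reader might infer that the plan does use current-day BSA, so that the index will rise. The documents do not support that: with height or baseline BSA the artefact is zero. This stands, and the size given here is conditional on it.
- **The index is one of three LA measures.** A reader might infer that the trial would wrongly conclude that remodeling did not improve. That goes too far. Diastolic grade and LA pressure are not listed as indexed and would also inform the conclusion. They do not measure size, however, so neither can replace the index in that role.
- **Ten percent is a goal.** A reader might infer that about half of any true benefit is lost. That requires a full 10% mean difference between arms. In the cited cohort 38% sustained such a loss, the echo follows six months of home-based maintenance, and controls may lose some weight too. The 5% rows may be nearer to what happens.
- **Raw volume is collected, so the harm is recoverable at analysis.** This is true, but only the index is named as an outcome. Choosing the measure after the data are seen would be open to challenge.
- **Indexing to current body size answers a legitimate question**, namely whether the atrium is large for the present body. That also stands as far as it goes. Remodeling, however, concerns change in the atrium itself, and the plan's rationale discusses LA volume as the risk marker.

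**Conclusion.** The point holds in conditional form. What the supplied text establishes is that the only atrial-size outcome has no stated denominator, that one arm has a weight-loss goal, and that the planned comparison has no adjustment for body size. If the index uses BSA at each echo, the contrast is biased against the intervention by about 2.2 to 2.6% for a 5% between-arm difference in weight loss, rising to 4.6 to 5.4% at the full goal. Only the between-arm difference in weight loss matters.

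The bias concerns one component of a secondary outcome and leaves the primary outcomes untouched. It can mask a benefit or mimic worsening, but with greater weight loss in the intervention arm it cannot create a false benefit. It is still worth settling before data are seen: the plan hopes for an improvement in LA remodeling, and the trial is meant to inform a larger one.

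**What to change.** In section 4, secondary outcome a, name the change in unindexed LA volume (mL) from baseline to one year as the analysed atrial-size measure. Section 5.4 item 9 already lists it: "measurements: LA volume, LA pressure, diastolic function, grade". Alternatively, keep an index but divide both echoes by height or by baseline BSA, and state the formula. Height is needed anyway for BMI, which is among the planned measurements: "Anthropometrics: Body mass index (BMI), waist circumference, neck circumference". Report the conventional current-day index descriptively, with its formula. Make sections 5.3 and 5.4 and the echo data sheet agree.

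The cost is one sentence in section 4 and a matching line elsewhere, with no new data or visits. The small downside is that the main result is less directly comparable with published index values, which the descriptive report largely covers.

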5.4 Data Analysis (and sample size)

This is a parallel, randomized control study. The researcher analyzing results will be blinded to the patient's group. A statistician will be hired to analyze data and a statistician from C2E2 (UBC) has reviewed the study design. Normally distributed data will be analyzed using repeated measures analysis of variance (ANOVA) to calculate changes over time (baseline, six-months, one-year) within each group. Between groups analyses on differences from baseline will be analyzed using independent *t*-tests. Statistical significance will be set *a priori* as *p*<.05. Continuous variables will be described by group using mean (SD) (or median (P25, P75) if the data are skewed); and categorical variables will be described by frequency (percent).

To calculate effect size for the intervention group, we considered the moderate effect sizes reported in exercise studies measuring cardiorespiratory changes (e.g., Huang et al. (2016) (40) reported a moderately high effect size of 0.64 for aerobic changes following an exercise program in older adults). Using G-power software (*alpha* = .05), the

sample size required to achieve 80% power to detect an effect is 22 per group (two-tailed, or repeated measures design) (44). Based on the data from Malmo and colleagues (26) reporting a large effect size (1.0) for the difference in time spent in AF pre- and post-exercise, a sample size of less than 10 participants would achieve a power of 80%. The AF studies to-date report low attrition rates. For example, Pathak et al. (19) reported 10% attrition in the risk factor intervention group, and Malmo et al.(26) reported a 0% attrition in the three-month interval-training program. Given that the Richmond Cardiac Rehabilitation program similarly reports low drop-out rates (of approximately 2%), we have allowed for greater than 10% attrition. Including 40 participants in the intervention arm, and 40 participants in the control arm will allow for more than 10% drop out while still maintaining adequate power to detect an effect.

6. Summary and Impacts on Practice

Richmond has experience in recruiting patients with AF, cardiac rehabilitation, and bariatric diet therapy program. Our Richmond team of specialists, combined with strong partnerships with our colleagues at VGH that have experience with research trials will help guide us in implementing a successful research project.

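### Stratified randomisation is mentioned without any factor, and the arms are compared by unadjusted t-tests; if real prognostic strata are balanced, those tests are conservative, and a baseline- and stratum-adjusted model should replace them

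*Combined protocol and SAP*

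**What the plan says.** Section 5.1 (Proposed Study Design) states that consenting patients "will be randomized and stratified to" the control or intervention arm. The next sentence gives the numbers and speaks only of randomisation: "Forty patients will be randomized to control arm and 40 patients randomized to the intervention arm". Nothing in the document names a stratification factor, a number of strata, a block size or a way of producing the allocation list.

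The between-arm analysis is one sentence in section 5.4 (Data Analysis (and sample size)): "Between groups analyses on differences from baseline will be analyzed using independent" t-tests. The other planned method, repeated measures ANOVA, is used "to calculate changes over time (baseline, six-months, one-year) within each group" and does not compare the arms. Neither method has a stratum term or a baseline covariate.

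**The concern.** When allocation is balanced within strata, differences between strata cannot contribute to the difference between arms. An independent t-test still counts that variation as error. Its standard error then exceeds the true sampling variability of the estimate, its intervals are too wide, and it rejects a true null less often than 5%.

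This would matter here because the planned size leaves little slack for a between-arm comparison, as shown under the working. A plan that takes the trouble to stratify and then ignores the strata gives up precision it has already secured. A plan that never meant to stratify misdescribes its design. Either way the two sections need to be brought into line.

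**Working it through.** **Inputs from the documents**
- Allocation 40 and 40 (section 5.1).
- Significance level: "Using G-power software (*alpha* = .05), the" (section 5.4, Data Analysis).
- Stated requirement: "sample size required to achieve 80% power to detect an effect is 22 per group (two-tailed, or repeated measures design").
- Effect size 0.64: the cited exercise meta-analysis "reported a moderately high effect size of 0.64 for aerobic changes following an exercise program in older adults".
- An allowance of more than 10% for drop-out (same section).

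The second planning effect, 1.0 for time in AF, is explicitly a before-after figure and is not used here.

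**Assumptions, because the documents give no figure**
- R², the share of variance in change from baseline explained by the strata, is taken from 0 to 0.30.
- 0.64 is treated as a standardised between-arm difference in change.
- Balance is enforced within strata.

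**Step 1: the plan's own figure.** A paired two-sided t-test at d = 0.64, 5% level and 80% power needs n = 21.16, rounded up to 22. The stated 22 therefore reproduces, but as a within-group calculation. For two independent arms the normal approximation is n = 2(1.960 + 0.842)² / 0.64² = 38.3, so 39 per arm. The noncentral t gives 39.3, so 40 per arm.

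**Step 2: power of the planned t-test, with no strata effect.** At 40 per arm it is 80.7%. After 10% loss, 40 × 0.90 = 36 per arm, and it is 76.4%.

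**Step 3: what ignoring balanced strata does.**
- Standard error inflation = 1/√(1 − R²).
- Real two-sided error = 2[1 − Φ(1.96/√(1 − R²))].
- Number per arm that would give an adjusted analysis the precision the t-test reports = 40(1 − R²).

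| R² | SE inflation | Real error, formula | Real error of t-test, simulated | Equivalent n per arm |
|---|---|---|---|---|
| 0 | 1.000 | 5.0% | 5.1% | 40 |
| 0.10 | 1.054 | 3.9% | 4.1% | 36 |
| 0.20 | 1.118 | 2.8% | 3.0% | 32 |
| 0.30 | 1.195 | 1.9% | 2.0% | 28 |

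The simulation used 10,000 trials per setting, 40 per arm and four equal strata balanced within stratum. The stratum-adjusted regression rejected 5.0% to 5.2% of true nulls throughout. At R² = 0.20 the t-test reported a mean standard error of 0.223 against a true 0.199. At R² = 0 the two agreed (0.222 against 0.223).

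**Step 4: power recovered by adjusting for the strata.** This uses d = 0.64/√(1 − R²) in the noncentral t.

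| R² | 40 per arm | 36 per arm |
|---|---|---|
| 0 | 80.7% | 76.4% |
| 0.05 | 82.6% | 78.4% |
| 0.10 | 84.6% | 80.6% |
| 0.20 | 88.5% | 84.9% |
| 0.30 | 92.2% | 89.3% |

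In the simulation at d = 0.64 and 40 per arm, t-test power against adjusted power was 79.9% and 80.0% at R² = 0, 81.4% and 83.9% at 0.10, 83.1% and 88.7% at 0.20, and 84.2% and 92.1% at 0.30. The gap therefore runs from nothing to about 8 percentage points.

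The further gain from adjusting for the baseline value is not in these figures. It depends on the correlation between baseline and follow-up, which the documents do not give.

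**The case against.** The strongest reply is that the loss is hypothetical. It needs allocation balanced within strata and strata that predict change, and the documents establish neither. Patients described as stratified to two arms may simply mean patients allocated to two arms, and the Data Analysis section describes a parallel randomised study without mentioning strata. The t-tests also work on change, so differencing may already have removed much of what a stable baseline factor explains. One or two unnamed factors cannot be presumed to predict change in Holter AF time, symptom scales, quality of life, echocardiography, risk factors, drug costs and emergency visits alike. All of this stands, and it is why the range must start at nil and be read outcome by outcome.

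It is also true that any error is on the safe side. The fall to 76% power at 36 per arm comes from attrition and would occur with no strata at all.

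The objection does not clear the plan. If stratification is intended, its factors are missing from both design and analysis. If it is not, section 5.1 needs correcting. The adjusted model costs almost nothing even when the strata carry no information: at R² = 0 its simulated power was 80.0% against 79.9% for the t-test.

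**Conclusion.** The point holds in conditional form. Stratification is stated but undefined, and the planned between-arm test would ignore it. If the strata are balanced and prognostic for change, standard errors are about 5% to 20% too wide and the real two-sided error is about 4% down to 2%, for an assumed R² of 0.10 to 0.30. At R² = 0 there is no loss.

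A reader might infer that the standard errors are certainly too wide for every between-arm outcome. The documents do not support that, because they name no factor and R² may be near zero for some or all outcomes. Nor should a reader infer bias or false positives: the treatment estimate is unaffected and the error rate falls rather than rises.

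The improvement is worth making because the margin is thin. At d = 0.64 the unadjusted test has about 76% power with 36 per arm, and adjusting for strata that explain 10% of the variance would bring it to 80.6%. The power figures rest on treating 0.64, a fitness effect, as a between-arm difference.

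**What to change.** For each continuous between-arm outcome, replace the independent t-test with a linear model (ANCOVA) of the follow-up value on arm and that outcome's baseline value, plus the stratification factors. In section 5.1, name one or two factors and the allocation method, fixed before the first randomisation; 80 patients will not support more than a few strata. If no stratification is intended, delete the word from section 5.1 and keep the baseline-adjusted model.

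The cost is analysis-plan wording, a stated allocation procedure, and one degree of freedom for the baseline value plus one for each two-level factor. That is two or three in all, taking the residual degrees of freedom from 80 − 2 = 78 to 76 or 75. The baseline values are already to be collected, so no new measurement is needed.
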